**Table 6.5. Summary of Analyses for Endpoints Related to Hypoglycemia**

Endpoint	Analysis Period	Statistical Method
Rate of hypoglycemic events (per patient per 30 days / year) 
 
All Documenteda
 
Nocturnala
 
Documented Symptomatica
 
Non-Nocturnal (Documented and occurred between waking and bedtime)a
 
	0-12, 0-26, 12-26 weeks	Negative binomial regression with treatment and log (exposure/30 days) or log (exposure/365.25 days) as the offset in the model.
Incidence of hypoglycemic events 
 
All Documenteda
 
Nocturnala
 
Documented Symptomatica
 
Non-Nocturnal ( Documented and occurred between waking and bedtime)a
 
	0-12, 0-26, 12-26 weeks	Logistic regression with treatment as an independent variable.
Rate of postmeal hypoglycemic events (per patient per 30 days / year) for all 3 main meals 
 
Documented Symptomatica
 
	$\leq 0.5$ , $\leq 1$ , $\leq 2$ , $\leq 4$ , $>1$ to $\leq 2$ and $>2$ to $\leq 4$ hours after start of a meal within 0-12,12-26, 0-26 weeks	Negative binomial regression with treatment and log (exposure/30 days) or log (exposure/365.25 days) as the offset in the model.
Incidence of postmeal hypoglycemic events for all 3 main meals 
 
Documented Symptomatica
 
	$\leq 0.5$ , $\leq 1$ , $\leq 2$ , $\leq 4$ , $>1$ to $\leq 2$ and $>2$ to $\leq 4$ hours after start of a meal within 0-12,12-26, 0-26 weeks	Logistic regression with treatment as an independent variable.

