5.1. Overall Design

[figure not shown]
Study I8B-FH-ITSE (ITSE) is a Phase 3, prospective, double-blind, randomized, multinational, multicenter, 2-group, parallel, active-controlled study conducted in patients with T2D currently treated with basal insulin in combination with at least 1 prandial insulin injection OR premixed insulin with at least 2 injections daily. Patients will be randomized to 1 of the 2 treatment groups in 2:1 ratio (LY900014: insulin lispro). Each of the treatment therapies, LY900014 and insulin lispro, will be administered immediately (0-2 minutes) prior to each meal in a double-blind manner. The study is designed to demonstrate noninferiority of LY900014 when compared with insulin lispro in change from baseline to Week 26 in HbA1c, when both are administered at the start of the meal. The study includes a 1-week screening period and an 8-week lead-in period, followed by a 26-week treatment period, and a 4-week safety follow-up period.

The purpose of the lead-in period (prior to randomization) will be to titrate basal insulin, obtain preliminary diagnostic laboratory tests, and determine baseline hypoglycemia rates. Patients treated with either a) basal insulin (insulin glargine U-100, insulin degludec U-100, insulin detemir or neutral protamine Hagedorn [NPH] insulin) in combination with at least 1 prandial injection of bolus insulin or b) at least 2 injections of premixed insulin will be eligible for inclusion in the trial.

Patients should use the same study basal insulin regimen throughout the trial, with allowed regimens as follows: insulin glargine U-100 (Basaglar/Abasaglar or LANTUS) once daily or insulin degludec U-100 once daily in accordance with local regulation. Patients using basal insulin regimens other than insulin glargine U-100 or degludec U-100 will be transferred at Visit 2 to an allowed study basal insulin regimen, which will be chosen by the investigator. Basal insulin will be titrated during the 8-week lead-in period using a titration algorithm to allow the patient to reach the target fasting blood glucose (FBG) by the end of this period.

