Patients treated with insulin aspart, insulin glulisine, regular human insulin, or premixed insulin will be transferred to insulin lispro at Visit 2, so that all patients will be treated with insulin lispro throughout the lead-in period. Patients treated with 1 to 2 prandial injections a day or premixed insulin prior to study entry will transition to 3 injections a day of prandial insulin lispro at the beginning of the lead-in period. At Visit 8, patients will be randomized to either LY900014 or insulin lispro at each meal. During the initial 12 weeks after randomization (intensive titration period), prandial insulin doses should be titrated as necessary in order to meet the target self-monitored blood glucose (SMBG) levels. Basal insulin may be titrated as needed to facilitate optimal prandial dosing or for safety reasons such as hypoglycemia or unacceptable hyperglycemia. Thereafter, during the maintenance period (Weeks 12-26 of treatment), it is expected that adjustments to prandial and basal insulin doses would be to maintain glycemic control or for safety reasons such as hypoglycemia or unacceptable hyperglycemia.

[Figure ITSE.1](#) illustrates the study design.

Abbreviations: T = telephone visit; wk = week.

- a At Visit 2, patients treated with insulin aspart, insulin glulisine, regular insulin, or premixed insulin will be transferred to insulin lispro. At Visit 2, patients treated with a basal insulin regimen other than insulin glargine U-100 or insulin degludec will be transferred to insulin glargine U-100 once daily or insulin degludec U-100 once daily. At Visit 8, patients will be randomized to either insulin lispro or LY900014 and continue their basal insulin regimen.
- b Titrate basal insulin.
- c Titrate prandial insulin (insulin lispro or LY900014).
- d Patients will discontinue study insulins at Week 26.

Figure ITSE.1. Illustration of study design for Clinical Protocol 18B-FH-ITSE.

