7.7.1. Management of Oral Antihyperglycemic Medications

During the study lead-in and treatment periods, patients may continue the use of up to **2 of the following OAMs: metformin, SGLT2 inhibitor in accordance with local regulations**. Please also refer to Exclusion Criterion [30] for criteria regarding thiazolidinediones, GLP-1 receptor agonists, and pramlintide (Section 6.2). Other prestudy OAMs including sulfonylurea,

meglitinide, DPP-4 inhibitor, and alpha-glucosidase inhibitor agents will be discontinued at the beginning of the lead-in period (Visit 2).

Oral antihyperglycemic medication dosing is to remain stable during study lead-in and treatment, except with the development of contraindications or for safety reasons. During study lead-in and treatment, all glycemic management is to be conducted by adjustment of basal and prandial insulin doses. In emergency situations, it may be necessary for patients to change their dose of OAM and/or be treated with a nonstudy insulin. This will be allowed for up to 14 consecutive days (Section 8.1.2).

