10.3. Statistical Analyses

10.3.1. General Statistical Considerations

Statistical analysis of this study will be the responsibility of Lilly or its designee. Any change to the data analysis methods described in the protocol will require an amendment ONLY if it changes a principal feature of the protocol. Any other change to the data analysis methods described in the protocol, and the justification for making the change, will be described in the SAP or the clinical study report (CSR). Additional exploratory analyses of data will be conducted as deemed appropriate.

The primary analysis is for the treatment period through Week 26.

Efficacy analyses will be conducted on all randomized patients using an intention-to-treat (ITT) approach according to the treatment the patients are assigned. Efficacy analyses, including the analyses for the primary and multiplicity adjusted objectives, will be performed, including data collected prior to permanent discontinuation of IP. When change from baseline is included as a response variable of analysis models, the patient will be included in the analysis only if a baseline and at least 1 postbaseline measurement are available. Selected efficacy analyses will also be conducted using the Per Protocol (PP) and Completer populations.

Safety analyses will be conducted on the Safety population. Analyses of AEs will include 2 sets of analyses, unless otherwise specified. The first set of analyses will include data collected prior to permanent discontinuation of IP. The second set of analyses will include all data collected during the course of the entire study including the follow-up visit, regardless of IP use. Analyses of hypoglycemia will use data collected prior to permanent discontinuation of IP; while analyses for post-treatment may be performed as needed. Analyses of safety laboratory measurements will be performed on all data during the planned treatment period regardless of IP use.

Unless otherwise noted, all tests of treatment effects will be conducted at a 2-sided alpha level of 0.05, and CIs will be calculated at 95%, 2-sided. All tests of interactions between treatment groups and other factors will be conducted at a 2-sided alpha level of 0.10.

A graphical approach for multiple comparisons (Bretz et al. 2011) will be used to strongly control the overall Type I error (2-sided alpha level of 0.05) for testing the treatment effect for the primary and multiplicity adjusted objectives.

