Hypoglycemia rates will be summarized for periods of 30 days, 1 year, and 100 years (severe hypoglycemia only). The rate of severe hypoglycemia per 100 years will be compared between treatment groups using the empirical method (details will be described in the SAP). For each of other categories of hypoglycemia, the number of hypoglycemia events during a specific period (rate) after randomization (for example, 0-12 weeks of treatment period) will be analyzed by using a negative binomial regression model. The model will include treatment and the baseline hypoglycemia rate (measured during lead-in) as a covariate. An offset defined as the log transformation of treatment exposure in the specific period (days)/365.25 days (or 30 days) will be included in the model to estimate the rate of hypoglycemia per year (or per 30 days). The proportion of patients with at least 1 hypoglycemic event in each category (incidence) during a specific period after randomization will be analyzed using a logistic regression model including treatment and baseline hypoglycemia rate value in the model.

Continuous safety variables, as well as the change from baseline for these variables, will be analyzed either by MMRM or ANCOVA models. For categorical variables, Fisher's exact test will be used to compare treatment groups unless otherwise specified.

The analyses for assessing immunogenicity data will be described in the SAP.

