### 3. Revision History

Statistical analysis Plan (SAP) Version 1 was approved prior to the first patient visit. Version 1 was based on the Protocol I8B-FH-ITSE (ITSE) approved on 27 June 2018.

The main changes of SAP Version 2 are listed below.

- Analysis period of from randomization to Week 26 (including all data regardless of IP use) was added for some of the safety analysis.
- Removed the baseline rate covariate from all hypoglycemia models as there were many critical outliers leading to inaccurate in the LSM and the biases were inconsistent.
- For adjustments of covariates, HbA1c stratum at Visit 7 is changed to HbA1c stratum at baseline to be consistent with the global study ITRN..
- COVID-19 related analyses are added.
- Weights of the graphical testing scheme for the multiple testing of this study are updated by simulation and team decision.

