#### 6.12.4.1. Hypoglycemic Events

Hypoglycemia events that occur during the study outside the MMTT will be captured using an paper diary starting from Visit 2 through Visit 801. Whenever hypoglycemia is suspected, the patient should record the blood glucose value, any associated symptoms, and the treatment administered in paper diary. A set of events is counted as 1 event in analysis if it consists of an originating event and subsequent continuing events as marked by the patient in paper diary, or the duration between adjacent events is  $\leq 30$  minutes. The event with the highest severity will be selected for analysis with severity determined in the order of: 1) it is a severe hypoglycemia, 2) it has symptoms of hypoglycemia reported, and 3) it has the lowest blood glucose value. If there are multiple events tied in all 3 aspects, the event with the largest number of non-missing responses to the questions of nocturnal hypoglycemia and postmeal time frame will be selected. If there are still multiple events tied, the latest event (based on data entry time) will be selected.

The following types of hypoglycemia events will be derived in the analysis data sets: documented hypoglycemia, severe hypoglycemia and nocturnal hypoglycemia. Only severe hypoglycemia will be collected as AEs and all episodes of severe hypoglycemia will be considered as SAEs. Documented hypoglycemia (including documented symptomatic hypoglycemia, documented asymptomatic hypoglycemia and documented unspecified hypoglycemia) will be based on blood glucose (BG)  $\leq 70$  mg/dL. In addition, documented clinically significant hypoglycemia with similar criterion as above documented hypoglycemia except for the threshold of BG  $< 54$  mg/dL will be summarized.

Table 6.5 provides detailed statistical methods for each endpoint related to hypoglycemia. For these analyses, hypoglycemia events prior to the discontinuation of IP will be summarized. Additional analyses for other types of hypoglycemic events not mentioned in the table and for the post-treatment period may be conducted as needed.

The incidence and number of episodes of hypoglycemia during the MMTT will be summarized by treatment and time relative to the meal ( $\leq 0.5$ ,  $\leq 1$ ,  $\leq 2$ ,  $\leq 4$ ,  $>1$  to  $\leq 2$  and  $>2$  to  $\leq 4$  hours after start of the meal) and analyzed by Fisher's exact test.

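### Does removing the lead-in hypoglycemia rate from the SAP's hypoglycemia models weaken the rate comparisons?

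*SAP*

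**What the plan says.** Protocol 10.3.4 describes the negative binomial model for the non-severe categories: "The model will include treatment and the baseline hypoglycemia rate (measured during lead-in) as a covariate". The logistic incidence models carry the same covariate. The severe-event rate is compared by an empirical method and never had it. Protocol 5.1 lists among the purposes of the lead-in to "determine baseline hypoglycemia rates".

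SAP Section 3 lists this deletion, with its reason, among the main Version 2 changes: "baseline rate covariate from all hypoglycemia models as there were many critical outliers leading to inaccurate in the LSM and the biases were inconsistent". Table 6.5 follows: "Negative binomial regression with treatment and log (exposure/30 days) or log (exposure/365.25 days) as the offset in the model" for rates, and treatment alone for incidence. The subgroup models in SAP 6.13.2 inherit this.

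Lead-in data are still gathered. Events are "captured using an paper diary starting from Visit 2 through Visit 801", and SAP Table 6.2 still defines the hypoglycemia baseline as Visits 2 to 8.

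Protocol 10.3.1 requires an amendment only when a principal feature changes. Any other change to the methods, "and the justification for making the change, will be described in the SAP or the clinical study report (CSR"). SAP 6.5 makes no multiplicity adjustment outside the primary and multiplicity-adjusted objectives, and hypoglycemia is not among those.

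**The concern.** A patient's earlier event rate is often the natural covariate for a later event rate, and here the trial measures it by design. Randomization is not stratified on it. Documented symptomatic hypoglycemia is a named secondary objective, and 2:1 allocation leaves only about 564/3 = 188 comparator patients. If lead-in and on-treatment rates are strongly related, leaving the covariate out widens the interval for the rate ratio and leaves chance imbalance in prior rate uncorrected.

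The stated reason also seems to aim at something else. Inaccurate LS means are a fault in the displayed group rates, not in the randomized ratio. If the rate was entered untransformed (the protocol does not give its scale), a log link turns a few extreme lead-in rates into very large predictions. Taking the logarithm and averaging predictions over patients would tame that. Deletion therefore looks like a heavier remedy than was needed, and no adjusted sensitivity analysis is specified.

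**Working it through.** **Inputs.** From the documents: 564 randomized 2:1, so 376 and 188; an 8-week (56-day) lead-in; a 26-week (182-day) treatment period; 15% dropout. The only design figure in the documents is for HbA1c, and it reproduces. SE = 1.1 × √(1/320 + 1/160) = 0.1065; 0.4/0.1065 − 1.96 = 1.80; power = Φ(1.80) ≈ 96%. Also 480/0.85 = 564.7, against 564 stated. Nothing comparable exists for hypoglycemia, so event rate, dispersion, correlation and outlier share below are all assumptions.

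**1. Is the rate ratio biased without the covariate?** With a log link, the mean per unit of exposure is E[Y | T, X] = exp(a + bT + cX). Randomization makes X independent of T, so E[Y | T] = exp(a + bT) × E[exp(cX)]. The last factor is common to both arms and cancels, leaving exp(b) as the rate ratio either way. Simulation agrees. With no true effect, the mean log rate ratio differed from the unadjusted one by at most 0.003 in every form. With a true ratio of 0.7, no form showed bias.

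**2. Are the unadjusted group rates accurate?** Lead-in counts do not enter the treatment-only model, so lead-in outliers cannot distort its rates. In the main simulations, without added outliers, they were within 0.5% of truth.

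**3. What precision is given up?** Main simulations: 0-26 weeks; 2, 6 or 12 events/year; dispersion 1 or 2; 2,000 runs per scenario. The table gives the empirical SE of the log rate ratio, log-covariate model divided by treatment-only model.

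| Correlation | Gamma frailty | Lognormal frailty |
|---|---|---|
| 0 | 1.000-1.003 | 0.995-1.002 |
| 0.3 | 0.987-1.001 | 0.964-0.998 |
| 0.5 | 0.961-1.000 | 0.890-0.986 |
| 0.7 | 0.891-0.987 | 0.800-0.971 |

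The paired Monte Carlo SE is 0.001 to 0.015, so ratios close to 1 cannot be told from no gain. The 0.800 needs lognormal frailty, 12 events/year, dispersion 2 and correlation 0.7 together. A smaller separate set gave 1.00 to 0.92 (gamma) and 0.99 to 0.67 (lognormal) at 10 events/year over correlations 0 to 0.8. At 2 events/year under gamma it found no gain (1.00 to 1.02).

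**4. Which correlation is plausible?** The documents do not say, but the protocol gives reasons to expect a weak one. Patients on one or two prandial injections or on premixed insulin "will transition to 3 injections a day of prandial insulin lispro at the beginning of the lead-in period" (Section 5.1). Section 7.7.1 states that sulfonylurea, "meglitinide, DPP-4 inhibitor, and alpha-glucosidase inhibitor agents will be discontinued at the" start of the lead-in. Basal insulin is titrated during the lead-in, and intensive prandial titration begins only after randomization.

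**5. How does the alternative behave under the problem the SAP names?** Gamma frailty, dispersion 2, correlation 0.7; 2% or 5% of patients given 20 to 60 extra lead-in events; predictions averaged over patients.

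| True rate/year | Outliers | Log covariate | Raw covariate |
|---|---|---|---|
| 2 | 2% | 2.09 (+4.5%) | 2.03 |
| 2 | 5% | 2.04 (+2.0%) | 2.00 |
| 6 | 2% | 6.37 (+6.2%) | 37.56 |
| 6 | 5% | 6.42 (+7.0%) | 6.07 |
| 12 | 2% | 12.52 (+4.3%) | 71.76 |
| 12 | 5% | 12.86 (+7.2%) | 13.40 |

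The raw column shows how erratic an untransformed covariate can be, which is consistent with the SAP's account without proving it. The log form is far better but not clean. Separate runs with 5-10% outliers gave 6.26-6.44 at true 6 and 12.80-12.81 at true 12, against unadjusted 6.02-6.04 and 11.98-12.05. Under lognormal frailty the log form's inflation was 1-3%.

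**6. Gain and distortion go together.** At correlation 0 to 0.3 the log form's rates stay within 0.7% of truth with 2% or 5% outliers, but there is little to gain there. With 5-10% outliers at correlation 0.3 under gamma, the SD ratio was 0.994-1.007. The distortion appears at 0.7, where the gain is largest.

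**The case for a change.** The best case for adjustment is that it costs almost nothing in precision. The worst SE ratio in any main or outlier run was 1.007 (Monte Carlo SE 0.005), and a ratio of 0.80 would be worth 1/0.80² = 1.56 times the sample. Log scale plus averaged predictions does cure most of the display problem. At a true rate of 10/year and correlation 0.6 it gave 9.9, against averages of 11.5 (gamma) and about 746 (lognormal) with the raw covariate. In one lognormal set with 3% outliers it stayed at about 10.0. A sensitivity analysis fixed before unblinding would also be more credible than one chosen afterwards.

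These points stand as far as they go. They show that an adjusted model is a reasonable alternative, not that the treatment-only model is wrong. The sponsor considered adjustment, reported trouble with it and dropped it. The documents do not say in which data the outliers were seen, but Protocol 7.3 keeps the study team blinded.

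The alternative also brings choices of its own: a constant for zero counts, and a rule for which Table 6.5 categories are common enough to adjust. Some rows would be adjusted and others not, although postmeal symptomatic hypoglycemia is equally a named secondary objective. Interval coverage does not separate the models. With robust standard errors it was 93.5-95.5% adjusted and 93.4-95.8% unadjusted. The lowest model-based figures, under lognormal frailty, were 87.0% and 85.7%, so that weakness is present with or without the covariate.

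**Conclusion.** The concern does not hold. Removing the covariate is a described and justified change of the kind Protocol 10.3.1 allows. It leaves a valid comparison with accurate group rates and touches no alpha-controlled test. The possible loss is precision in descriptive rate ratios. On assumed inputs that runs from nothing to an SE ratio of 0.80 in the most favorable corner of the main simulations; under gamma frailty with correlation up to 0.5 it is at most about 4% (0.961). Against this, the log-covariate alternative can put group rates up to about 7% too high when lead-in outliers are present and the correlation is high. That partly restores the inaccuracy the SAP set out to avoid.

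This is a choice between two defensible estimators. An adjusted exploratory analysis remains open under SAP 6.1 if the sponsor wants one. The conclusion rests on assumed event rates, dispersions, correlations and outlier shares. Only the negative binomial rate models were simulated, not the logistic incidence models.

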**Table 6.1. Patient Populations**

Population	Description
Entered	All patients who give informed consent.
Enrolled	All patients who receive at least 1 dose of open-label insulin lispro in the 8-week lead-in period.
Randomized	All patients who are randomly assigned to study treatment at Visit 8. Treatment group will be defined on the basis of the treatment the patients are assigned.
Safety	All randomized patients who receive at least 1 dose of the randomly assigned investigational product (IP). Treatment group will be defined on the basis of the treatment the patients are assigned.
Completer	Patients included in the randomized population who have completed Week 26 of study treatment without permanent discontinuation of IP. Treatment group will be defined on the basis of the treatment the patients are assigned.
Per Protocol	Patients included in the randomized population who have completed Week 26 of study treatment without permanent discontinuation of IP and without significant protocol deviations through Week 26 that would significantly impact the primary objective. Treatment group will be defined on the basis of the treatment the patients actually receive.

Unless otherwise stated, the efficacy analyses will be conducted on the Randomized Population, and the safety analyses will be conducted on the Safety Population.

The primary analysis is for the treatment period through Week 26.

Unless otherwise noted, all tests of treatment effects will be conducted at a 2-sided alpha level of 0.05, and CIs will be calculated at 95%, 2-sided. All tests of interactions between treatment groups and other factors will be conducted at a 2-sided alpha level of 0.10.

The definitions of baseline and post-baseline for the efficacy and safety analyses depend on which analysis period is being used. The following analysis periods will be used:

- Lead-in Period – Visits 2 to 8
- 26-Week Treatment Period – from randomization to Week 26 prior to discontinuation of investigational product (IP)
- 
- 26-Week Treatment Period and Safety Follow-Up Visit – from randomization to Visit 801 (including all data regardless of IP use)

The data on IP is defined based on the following rules:

- For data only measured at an office visit
  - Mixed-meal tolerance test (MMTT) postbaseline data will be classified as on IP if the MMTT performance date is prior to or on the last IP dose date

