**Baseline and Post-Baseline Definitions and Patient Population by Study Period and Type of Analysis**

Study Period/Analysis	Patient Population	Baseline Observations	Post-Baseline Observations
1,5-AG	All Randomized Patients with a baseline and at least one post-baseline observation	Visit 8 prior to initiation of IP	Visits 11, 15, and 18 prior to discontinuation of IP AND Last of Visits 9-18 prior to discontinuation of IP

Health outcomes: ITSQ, EQ-5D-5L, EQ- VAS, WPAI-GH	All Randomized Patients with a baseline and a post- baseline observation	Last of Visits 1-8	Last of Visits 9-18 prior to discontinuation of IP
Safety Laboratory Tests (chemistry, hematology, lipids) – continuous analysis	All Patients in the Safety Population with a baseline and a post-baseline observation	Last of Visit 1-8	Visit 18 (planned) AND last of Visits 9-18 (planned including early discontinuation visits) regardless of IP use
Safety Laboratory Tests (chemistry, hematology, lipids) – categorical analysis	All Patients in the Safety Population with a normal baseline (with respect to the direction being analyzed) and a post- baseline observation	Visits 1-8 (including unplanned tests)	Visits 9-18 (including unplanned tests) regardless of IP use
TEAEs	All Patients in the Safety Population	Prior to first dose of randomized IP (or Visit 8 date if the dose date is missing) but after the first dose of open-label insulin lispro in the Lead-in Period	From first dose of randomized IP to last dose of randomized IP AND From first dose of randomized IP to Visit 801
Hypoglycemia events	Safety Population	All Visits 2-8	All Visits 9-18 prior to discontinuation of IP
Weight and vital signs	All Patients in the Safety Population with a baseline and a post-baseline observation	Last of Visits 2-8	Visits 9-18 prior to discontinuation of IP AND Visits 9-801 regardless of IP use
Anti-insulin lispro antibodies	Safety Population	Visit 2	Visits 3-801 regardless of IP use

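### As Tables 6.2 and 6.5 read, patients who stop IP before Week 12 stay in the Weeks 12-26 hypoglycemia incidence denominator as event-free

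*SAP*

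**What the plan says.** SAP Table 6.5 lists incidence of all documented, nocturnal, non-nocturnal and documented symptomatic hypoglycemia for the periods "0-12, 0-26, 12-26 weeks". The method is "Logistic regression with treatment as an independent variable". Postmeal and severe incidence use the same treatment-only model.

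The rate analyses in the same table use "Negative binomial regression with treatment and log (exposure/30 days) or log (exposure/365.25 days) as the offset in the model". Protocol section 10.3.4 makes clear that this offset is the exposure within the period analysed.

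The denominator comes from SAP section 6.1 and Table 6.2. By default "the safety analyses will be conducted on the Safety Population", which needs only one dose of randomized IP. The hypoglycemia row of Table 6.2 names that population with no further condition, while several other rows also require a post-baseline observation.

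The numerator comes from the same row, which limits the data to "All Visits 9-18 prior to discontinuation of IP". SAP section 6.12.4.1 repeats it: "For these analyses, hypoglycemia events prior to the discontinuation of IP will be summarized". Under section 6.1, dated diary entries count up to one day after the last dose.

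Protocol section 10.3.4 describes the endpoint as "The proportion of patients with at least 1 hypoglycemic event in each category (incidence) during a specific period after randomization". Neither document defines who is at risk in a given period.

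**The concern.** Take a patient who stops IP at Week 5. The denominator rule keeps this patient in the Weeks 12-26 analysis. The numerator rule means no event from that window can count, even if the patient stays in the study and has one. Followed literally, the patient is scored as having had no hypoglycemia over 14 weeks that were never observed on treatment.

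The rate model for the same window cannot include this patient, because the log of zero exposure is undefined. Two analyses of one period would then rest on different patients without the plan saying so.

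Two things are at stake. The reported Weeks 12-26 percentages would be too low in both arms. If one arm stops IP more often, that arm would also look safer on incidence with no difference in risk.

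**Working it through.** **Plan figures.** The documents give no hypoglycemia incidence, event rate or timing of IP stopping. The one usable figure is the 15% dropout over 26 weeks (Protocol 10.1, SAP 5.2). It reproduces: 564 × 0.85 = 479.4, against 480 completers. Using it for IP stopping is an assumption. Protocol 5.2 speaks of completing treatment, and 10.1 of completing the study.

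**Share with no exposure in Weeks 12-26 (f).**
- Constant hazard: f = 1 − 0.85^(12/26) = 7.2%, or 564 × 0.072 ≈ 41 patients.
- Evenly spread stopping: f = 0.15 × 12/26 = 6.9%, or about 39 patients (26 LY900014, 13 lispro).
- Extremes: 0% if all stop after Week 12, and 15% (about 85 patients) if all stop before.

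**Effect on the percentage.** If p is the incidence among patients with on-IP exposure in the window, the as-written figure is p × (1 − f). The relative understatement is f, about 7% (range 0% to 15%).

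**Assumed event model.** Negative binomial counts with rate r per year and dispersion k, so the probability of at least one event over t years is 1 − (1 + k·r·t)^(−1/k). Stopping times are exponential, and this probability is averaged over them. Two cases: r = 2, k = 2; and r = 6, k = 1.5. At 15% stopping:

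| | r = 2, k = 2 | r = 6, k = 1.5 |
|---|---|---|
| Weeks 12-26, exposed patients only | 29.5% | 54.3% |
| Weeks 12-26, as written (× 0.928) | 27.4% | 50.4% |
| Weeks 0-26, full exposure | 42.2% | 67.8% |
| Weeks 0-26, as written | 39.8% | 64.9% |

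Every Safety patient has some exposure in Weeks 0-12 and 0-26, so only partial exposure acts there.

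**Effect on the comparison, no true difference.** The odds ratio is a/(1 − a) divided by b/(1 − b), with the arm that stops more often in the numerator.

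| IP stopping by Week 26 | Weeks 12-26, as written | Weeks 12-26, exposed only | Weeks 0-26 |
|---|---|---|---|
| 15% vs 15% | 1.00 | 1.00 | 1.00 |
| 16% vs 14% | 0.97-0.98 | 0.99 | 0.98-0.99 |
| 20% vs 10% | 0.86-0.90 | 0.96 | 0.91-0.93 |

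Example at 20% vs 10%: f = 1 − 0.80^(12/26) = 9.8% and 1 − 0.90^(12/26) = 4.7%. With r = 6 and k = 1.5, incidence reads 48.5% vs 52.2%, odds ratio 0.86.

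**False-positive rate.** Suppose f is 10% (LY900014, n = 376) vs 5% (lispro, n = 188) and p = 60% in both. The figures become 60% × 0.90 = 54% and 60% × 0.95 = 57%, odds ratio 0.89. The standard error of the log odds ratio is √(1/(376×0.54) + 1/(376×0.46) + 1/(188×0.57) + 1/(188×0.43)) = 0.180, so the mean z is about −0.67. The two-sided 5% test then rejects about 10% of the time.

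**With a true difference and equal stopping.** At f = 6.9%, 60% vs 50% (odds ratio 0.667) reads as 55.8% vs 46.5% (0.688), a mild attenuation.

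**The case against.** - **The coding is inferred.** A reader might take the SAP to say that early stoppers are scored event-free. It does not. That follows from combining the denominator and numerator rules, and a programmer could instead reuse the rate model's risk set. This stands, but no rule in the plan directs that choice.
- **The named endpoint is a different window.** A reader might infer that the secondary objective itself counts patients with no time at risk. It does not, because it runs from baseline to Week 26 and every Safety patient has exposure there. Weeks 12-26 is an additional period in Table 6.5. This stands and narrows the point.
- **Comparative bias needs unequal stopping.** The plan assumes one 15% figure, and both arms receive a lispro formulation under double blind. Nothing in the documents suggests 20% versus 10%. This stands.
- **The logistic model fits the stated endpoint**, a percentage of patients with an event. A reader might conclude that it should be replaced. That would exchange a proportion for a hazard-type measure, a change of target that the documents do not call for.
- **Other outputs would help a reader notice the problem.** Rates carry an exposure offset, SAP 6.6 compares time to treatment discontinuation, and SAP 6.12.1 summarizes exposure. These endpoints are also outside the multiplicity-adjusted family (SAP 6.5). This limits the stakes but does not correct the Weeks 12-26 percentage.

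**Conclusion.** The point holds for Weeks 12-26. As the two tables read, patients without time at risk count as event-free, and the rate and incidence analyses of that window use different denominators. Under the plan's 15% applied to IP stopping at a constant hazard, about 7% of patients are involved and incidence is about 7% too low in relative terms in each arm.

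The comparison between arms is a conditional concern. With equal stopping and no true effect there is no bias. At a small imbalance (16% vs 14%) it is slight, and at an assumed 20% vs 10% it is noticeable. For the baseline-to-Week 26 endpoint the effect is smaller and comes from partial exposure alone. Event rates, dispersion and stopping patterns are all assumptions, because the documents supply none.

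The documents do not support saying that the incidence comparison favours either product, or that the logistic model is invalid. The change is worth making because the denominator is unstated and the remedy is cheap.

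**What to change.** 1. In SAP Table 6.5, restrict the Weeks 12-26 incidence analyses to Safety patients with on-IP exposure in that window, so that they match the rate model.
2. Report the number at risk by arm for each period.
3. Keep the logistic model as the stated analysis. Beside it, as a sensitivity analysis for each period, add an exposure-aware model: complementary log-log with log on-IP exposure as offset, or time to first event. The restriction in step 1 does nothing for Weeks 0-12 and 0-26, so partial exposure there is addressed only by this model.

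The cost is a few lines of SAP text and minor programming, since exposure by period is already derived for the rates. Protocol 10.3.1 allows such a change without an amendment unless it alters a principal feature.

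Three downsides should be stated. The Weeks 12-26 comparison then conditions on staying on IP to Week 12, a post-randomization event. The offset assumes a constant hazard within the period, which is doubtful across the titration and maintenance phases of Weeks 0-26. The supplementary estimate is a hazard-type ratio (a hazard ratio if time to first event is used), so it will not match the odds ratio numerically.
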